9. Self-Efficacy for Exercise Scale is used to evaluate how strongly patients feel they can exercise in the face of common barriers. There are 9 items with 10 choices ranging from 0 meaning no confidence to 10 meaning very confident they could/would exercise despite the barrier. Reliability was demonstrated with a alpha coefficient of 0.93 and validity, by factor loadings of all 9 items greater than 0.50 and path coefficients greater than 0.70.^{56,57} This scale has been validated in a group healthy minority older adults and in a group of older adults ~85+ living in a retirement community (Caucasian, female and unmarried).^{56,57}

10. Outcome Expectations for Exercise Scale-2 is used to measure positive and negative expectations for engaging in exercise. There are 13 items with 5 choices on a scale range from 1 strongly agree, 2 agree, 3 neither agree or disagree, 4 disagree, 5 strongly disagree. There are 2 subscales, one for the positive (9 items) or benefits

expected by engaging in exercise and the other on possible negative (4 items) outcomes from exercise. The each sub scale is then summed and divided by the number of items giving you an average score for positive and negative expectations score.⁵⁸ Validity was demonstrated by factor and Rasch analysis with a caveat of the negative subscales loaded on 2+ concepts suggesting some overlap.⁵⁸ Internal consistency of both subscales was 0.93 for positive and 0.80 for the negative.⁵⁸ Reliability score was 0.98 and 0.91, respectively.⁵⁸

11. Repeated Sit to Stand Test is an objective physical test in which the person is asked to rise from a seated position 5 times as quickly as possible. This measures leg strength as well as balance and mobility.^{59,60} A systematic review was completed and found this test is good to high test-retest reliability using interclass correlations of 0.76-0.99 across studies, in most populations and settings.^{59,61,62} Excellent interrater reliability was demonstrated with interclass correlation of 0.99 across multiple clinicians in multiple health care settings.⁶⁰⁻⁶² Poor performance on this test is associated with disability.⁶³

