12. Timed up and Go Test (TUG) is an objective measure of physical functional status is a simple technique for evaluating competence in basic activities. The test measures in seconds how long it takes for someone to, stand up from a chair, walk forward 10 feet, turn around, walk back to the chair, and sit down.⁶⁴ Reliability was been demonstrated by test-retest interclass correlations of 0.978-0.99 across studies done within 7 days.⁶⁵ Construct validity is acceptable with the measure demonstrating a specificity ranging from 87-97% and sensitivity from 83-87% for predicting older adults likely to fall.^{66,67} With 12.3 seconds as the cut off score for predicting falls in the ensuing 6 month time frame with no ceiling effect demonstrated.⁶⁶ TUG scores changed following a quadriceps and hamstrings strengthening program for patients with rheumatoid arthritis compared with subjects who received no strengthening. A reduction in time greater than or equal to 1.4 seconds is a major change and 0.2 is an unimportant change.⁶⁸

13. The Brief Pain Inventory Short Form (BPI-SF) is used to assess pain intensity and interference along with currently used pain management therapies. The BPI-SF assesses: intensity of pain through four items rated from 0 (no pain) to 10 (worst pain imaginable) that are averaged into one intensity score, current treatments being used (one item, open ended question), perceived pain relief (one item rated on a 0 to 100% scale), and extent that pain interferes with daily living through seven items rated from 0 (no interference) to 10 (completely interferes) that are averaged into one interference score.^{69,70} The interference questions assess two types of interference with daily activities: affective social functioning (e.g., interaction with others) and physical functioning (i.e., ability to carry out daily activities).^{69,70}

The 15-item BPI-SF was developed for cancer pain patients, but has shown consistent validity and reliability for many conditions.⁷¹ Reliability in arthritis and low back pain patients is .82 for severity scale and .95 for the interference scale.⁷² Reliability in osteoarthritis patients for both severity and interference scales is 0.80 or greater.⁶⁹ The BPI-SF is recommended for chronic pain clinical trials by IMMPACT.⁷³

14. The Patient Health Questionnaire (PHQ-8) was used to measure depression. The PHQ-9 is based on the Diagnostic and Statistical Manual of Mental Disorders for clinical

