depression diagnostic criteria.⁷⁴ Participants were asked to rate each of the 8 items by how often they had been bothered by the item over the past two weeks. The items are on a scale of 0= not at all, 1=several days, 2=more than half the days, 3=nearly every day. Time for participants to self-administer the instrument is less than 5 minutes (Kroenke, 2001).⁷⁴ A total score of ≥ 10 has been shown to have a sensitivity and specificity of 88% in diagnosis of major depression and we used this cut off in this analysis.⁷⁴ Due to the false positive reports on the last question of the PHQ-9, the PHQ-8 has been recommended as the validity and reliability remain the same as the PHQ-9 with correlation of 0.997, sensitivity of 50%, and specificity of 90%.⁷⁵

Table of variables and when they are obtained

| Variable | When Collected |
|--|----------------------------------|
| Demographics, clinical data, Charlson | Once Pre |
| DXA (muscle mass) | Pre, post, 6 months |
| Dynamometer-Strength and torque (muscle) | Pre, post, 6 months |
| 6-MWT (exercise capacity) | Pre, post, 6 months |
| ActivPal (time spent active) | Pre, post, 6 months |
| MSAS-HF (HF symptoms) | Pre, post, 6 months |
| MLHFQ (HF quality of life) | Pre, post, 6 months |
| Telephone interviews | Weekly during intervention phase |
| Promis Fatigue | Pre, post, 6 months |
| Self-Efficacy for Exercise Scale | Pre, post, 6 months |
| Outcome expectations for Exercise Scale | Pre, post, 6 months |
| Repeated Sit to Stand | Pre, post, 6 months |
| Timed up and go | Pre, post, 6 months |
| Self-Care of Heart Failure Index | Pre, post, 6 months |
| Brief Pain Inventory | Pre, post, 6 months |
| PHQ-8 | Pre, post, 6 months |
| Compliance Data from EMPI machine | Once post |

Section 6: Reporting of Adverse Events or Unanticipated Problems involving Risk to participants or others

The following standard definitions will be used for this study:

Adverse Event (AE)

Any untoward or unfavorable medical occurrence in a human study participant, including any abnormal sign (e.g. abnormal physical exam or laboratory finding), symptom, or disease, temporally associated with the participants' involvement in the research, whether or not considered related to participation in the research.

Serious Adverse Event (SAE)

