The research associate will review all data collected for completeness and readability, correcting any errors prior to data analysis. We will collect "reason for drop out" if a participant stops the study. We will continue to try to schedule subsequent data collection interviews even if the participant is not able to complete a previous one. During each data collection session, team members will work with participants to encourage response to all items and will review data to ensure all data points are completed unless the participant prefers not to answer. Nonetheless, missing data will occur and this will be acknowledged in the analysis.⁷⁶ We will conduct initial analyses using the maximum likelihood approach, as it emphasizes the use of all available data. The use of random effects modeling techniques, in particular repeated measures mixed modeling, allows for missing data by adjusting the estimation process to account for bias resulting from data missing at random. Baseline data from those with and without missing data will be compared to determine whether there are systematic differences, using demographic and personal variables. If the data are not amenable to the maximum likelihood method random effects analysis, multiple imputation will be used as an alternative procedure for handling missing data. Multiple imputation produces results similar to maximum likelihood when used under identical conditions. We will use multiple imputation in the sensitivity analyses; this will allow for the comparison of study results under a variety of assumptions to assess the robustness of the findings.

Statistical Analysis

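### The plan gives no rule for a participant who attends but cannot complete the sit-to-stand or Timed Up and Go, so a known poor result defaults to missing-at-random handling

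*Combined protocol and SAP*

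**What the plan says.** - **Sit-to-stand (Section 5, item 11):** "the person is asked to rise from a seated position 5 times as quickly as possible". No unit, time limit or score for an incomplete test is given. The item adds: "Poor performance on this test is associated with disability".
- **TUG (Section 5, item 12):** "The test measures in seconds how long it takes for someone to, stand up from a chair, walk forward 10 feet", then turn, return and sit. The benchmark is also in seconds: "A reduction in time greater than or equal to 1.4 seconds is a major change and 0.2 is an unimportant change". Again there is no score for inability.
- **Timing (table of variables):** "Repeated Sit to Stand | Pre, post, 6 months", and the same for TUG.
- **Missing data (Section 8):** "We will conduct initial analyses using the maximum likelihood approach, as it emphasizes the use of all available data". The mixed model is said to be one that "allows for missing data by adjusting the estimation process to account for bias resulting from data missing at random". Multiple imputation is the fallback and the sensitivity analysis; no scenario for inability, or for data not missing at random, is named. A reason is collected when a participant stops the study, but not when a single test is not completed.
- **Model (Section 8, Statistical Analysis):** a separate Time by Group repeated measures model for each outcome, with a transformation such as the logarithm if an outcome is not normal.
- **Eligibility (Section 3):** sedentary heart failure patients living at home. No minimum ability to stand or walk is set.

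**The concern.** A test that yields a time only on completion has no value for someone who cannot complete it. TUG is such a test by its stated unit. Sit-to-stand is presumably one too, since a fixed number of rises done at speed is naturally scored as a time, but the plan does not say so.

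A blank for this reason is not like a missed visit. The participant came, tried, and the outcome was observed to be poor. Missing at random would replace it with a finite time predicted from the people who could do the test. A participant who moves from unable to able then adds a slow follow-up time without full credit for the gain. One who loses the ability takes a bad result out of the later mean.

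The trial targets people whose muscle wasting and poor tolerance keep them from exercising, so these transitions could occur and could differ by arm. Because no reason is recorded for an uncompleted test, a physical failure could not later be told apart from a refusal.

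**Working it through.** **1. The plan's own figures.** No stated figure concerns these two tests. The general power statement was reproduced with N = 54, 3 visits and a noncentral F:

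- Group effect: λ = 54 × 3 × f² / (1 + 2ρ), df 1, 52
- Interaction: λ = 54 × 3 × f² / (1 − ρ), df 2, 104

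The plan gives no value for ρ. At ρ = 0.33:

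| Effect | Stated | Reproduced |
|---|---|---|
| Main, f = 0.4 | 97% | 97.2% |
| Main, f = 0.25 | 69% | 67.9% |
| Interaction, f = 0.25 | 95% | 93.9% |

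Two things follow. The figures assume 27 analysable participants per arm, so each uncompleted test lowers the number behind them. They also match the plan only for ρ of about 0.31 to 0.34, so a low correlation is a fair case to include below.

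**2. Direction in simple means (assumed inputs).** Able participants average 15 s, u of 27 are unable at baseline, and r of these recover to 25 s. The follow-up mean of the observed times rises by r × (25 − 15) / (27 − u + r):

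- u = 3, r = 1: 10/25 = 0.40 s
- u = 3, r = 2: 20/26 = 0.77 s
- u = 5, r = 3: 30/25 = 1.20 s
- u = 5, r = 5: 50/27 = 1.85 s

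Recovery therefore looks like worsening. The planned model does not compare raw means, so step 3 is the relevant one.

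**3. Likelihood on all available data (simulated, assumed inputs).** There are 27 per arm and two visits. Able participants have mean 15 s, SD 4. Recovery occurs in the stimulation arm only, to about 25 s, SD 3. Estimated gain when able participants truly gain 2.0 s:

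| Unable at baseline per arm / recovering | ρ = 0.7 | ρ = 0.3 |
|---|---|---|
| 0 / 0 | 2.0 s | not run |
| 3 / 1 | 1.90 s | not run |
| 3 / 2 | 1.67 s | 1.28 s |
| 5 / 3 | 1.53 s | 0.94 s |
| 5 / 5 | 1.30 s | 0.42 s |

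With a true gain of 1.0 s in able participants and 3 of 27 per arm unable, the estimate is roughly 0.1 s (ρ = 0.3) to 0.8 s (ρ = 0.8). With a slower recovered time of 28 s and all three recovering, a single-arm version gives a gain of 0.22 s at ρ = 0.5, 0.52 s at 0.7 and 0.67 s at 0.8. At ρ = 0.3 the change is +0.09 s, which is about zero.

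The correlation matters because the model uses the slow follow-up time to infer a slow baseline. This offsets part of the shift, and more of it when ρ is high.

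**4. The same kind of case with inability kept.** Take 24 participants going from 15 s to 14 s, and 3 going from unable to 28 s. In rises per second (5/time, unable = 0, everyone in a subgroup given its average time):

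- Before: (24 × 5/15 + 3 × 0) / 27 = 0.296
- After: (24 × 5/14 + 3 × 5/28) / 27 = 0.337

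The change is +0.041, in the right direction. It exceeds the +0.024 (5/14 − 5/15) among the 24 alone, because the three recoveries now count.

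**The case against.** **Inability may be rare or absent.** Participants live at home, travel to visits, do 50 dynamometer kicks and walk for six minutes. The documents give no rate of inability, and 3 to 5 of 27 is an assumption. This stands: if everyone completes both tests, nothing is lost.

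**The plan is silent; it does not prescribe missing at random for failed tests.** This also stands. That handling is the default consequence of having no other rule. The sensitivity analyses could in principle cover inability, but no such scenario is named.

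**The tests carry little weight.** Neither is assigned to a numbered aim. Strength is assessed by dynamometer and exercise capacity by the 6-minute walk, and the study describes itself as exploratory. This limits the severity.

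Three stronger readings are tempting, and the documents do not support them.

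- *The analysis would reverse a benefit.* In the case in step 4 of the working, the observed mean goes from 15.0 s to (24 × 14 + 3 × 28)/27 = 15.56 s although everyone improved. That compares raw means over different people, which the plan does not do. Under the planned type of model the gain shrinks, at worst to about nothing; a reversal is not shown.
- *The bias runs against stimulation.* It does so only if more participants recover the ability in that arm. Recoveries under sham, or losses of ability under stimulation, push the other way.
- *Scoring inability as 0 raises power.* One simulation (27 per arm, rate mean 0.33/s, SD 0.12, correlation 0.8, gain 0.06/s, 10% unable) gave 60% for seconds among completers, 72% for rate among completers and 71% for rate with unable = 0. The difference comes from the change of scale. Log time, which the plan already allows, gave 68%. The case rests on bias, not on power.

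**Conclusion.** The concern holds as a gap in the plan: inability to complete either test has no code and no analysis rule, and by default an observed poor result would be treated as an unseen ordinary one. A log transformation does not help, because there is no time to transform.

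The direction depends on which arm has more transitions between unable and able. The size depends on how many transitions there are and on the within-person correlation. Under recovery in the stimulation arm only, with 3 of 27 per arm unable, a true 1.0 s gain is estimated at roughly 0.1 to 0.8 s. For scale, the plan calls 1.4 s a major change on TUG, although the simulated times were chosen to resemble sit-to-stand. All inputs except the arm size are assumed, and that seconds is the unit for sit-to-stand is an inference. Because both tests are supporting measures, this is a minor to moderate improvement and does not affect the measures named for the aims.

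**What to change.** 1. **Record it.** At each visit, code each test as completed (with time), unable for physical reasons, refused, or not attended. This has to be done at the visit, since it cannot be reliably reconstructed afterwards.
2. **Prespecify an analysis that keeps inability as an outcome.** One option is sit-to-stand as 5/time and TUG as 20 ft/time (10 ft out and 10 ft back), with unable = 0, in the planned Time by Group model. A worst-rank analysis is an alternative.
3. **State the unit for sit-to-stand** and exempt zero-scored outcomes from the log transformation.
4. **Keep missing-at-random handling for unattended visits.** Report seconds among completers, and the number unable by arm and visit, descriptively.

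The cost is one status field and one derived variable per test, and a sentence or two in Section 8. There are two downsides. The analysed effect is no longer in seconds, so the 1.4 s TUG benchmark applies only to the descriptive table. A cluster of zeros may also make the distribution less normal, in which case worst-rank is the safer choice, although it credits a few recoveries only slightly: with no other effect and 5 of 5 recovering, the simulated chance that a stimulation participant does better at 6 weeks was 0.523 against 0.499 with no recovery.
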